#### **8.4.3 AE and SAE Collection**

All AEs and SAEs will be collected from the signing of the informed consent form until the one-year follow-up visit at the time points specified in the SoA (Section 1.3) as required by applicable regulation and best practice.

All SAEs will be recorded and reported to the sponsor and the pharmacovigilance team at Advanced Clinical within 24 hours of the study personnel becoming aware of the event. Please utilize the approved SAE data collection forms provided by Advanced Clinical to submit the notifications and updates. The investigator will submit any updated SAE data to the sponsor within 24 hours of it being available.

Investigators are not obligated to actively seek AE or SAE after conclusion of the study participation. However, if the investigator learns of any SAE, including a death, at any time after a subject has been discharged from the study up to a 30 day follow-up period, and he/she considers the event to be reasonably related to the study intervention or study participation, the investigator must promptly notify the sponsor.

#### **8.4.4 Follow-up of AEs and SAEs**

After the initial AE/SAE report, the investigator is required to proactively follow each subject at subsequent visits/contacts. All AE/SAEs, will be followed until resolution, stabilization, the event is otherwise explained, or the subject is lost to follow-up (Lost to follow-up is defined in Section **Error! Reference source not found.** of the protocol).

#### **8.4.5 Adverse Event and Serious Adverse Event Reporting**

Adverse events and serious adverse events will be reported to the FDA, the Sponsor and IRB in accordance to standard policy. These will be listed per site and reviewed by the Site PI, Contract Research Organization (CRO), study monitors, Sponsor's Medical Monitor and the Data Safety Monitoring Board (DSMB).

#### **8.4.6 Investigational New Drug (IND) Safety Reports**

Written Investigational New Drug (IND) safety reports will be submitted to the FDA by the IND sponsor, for serious unexpected adverse reactions within 15 calendar days of learning of its occurrence. If the event is fatal or is deemed to be life threatening, the report will be made within 7 calendar days.

#### **8.4.7 Unanticipated Problems (Emory IRB Requirement)**

The IND sponsor will make an assessment of whether an adverse event constitutes an unanticipated problem (UP) posing risks to subjects or others, per the Emory IRB Reportable Events guidelines. The IND Sponsor's assessment will be provided to the Emory IRB, which in turn will make a final determination. If the Emory IRB determines the event is an UP it will notify the appropriate regulatory agencies and institutional officials. Reporting of the Emory IRB's final determination should be submitted to the site's IRB of record per their policies and guidelines. See MILES Study Operations Manual for further details regarding reporting process.

### **9.0 Statistical Considerations**

#### **9.1 Statistical Hypothesis**

An experienced statistician trained in multicenter clinical trials has provided statistical justification. De-identified early pilot data, outside of this study, from the Emory Department of Orthopedics provided sample data for estimation.

Rigorous statistical analyses were performed based on the preliminary data with autologous MSC cell injections and data in the literature to design a randomized controlled study that will provide sufficient power to compare data from four different sites. The collaborative work will involve recruitment sites with an established track record in using stem cells for the treatment of knee osteoarthritis. In addition, these sites have a large clinical volume to complete the study as proposed.

While 120 subjects per site would provide sufficient power to achieve statistical differences, this number reflects a conservative estimate compared to the number of subjects that each site recruits for stem cell injections per year based on retrospective evaluations. The sample size of 120 subjects amongst 4 sites for each of the four arms is substantially greater than the other less rigorously controlled trials and the number also accounts for reasonably unlikely yet unforeseen variability between recruitments.

#### **9.2 Sample Size Determination**

The total estimated sample size for the proposed intention-to treat, parallel-group, multicenter, randomized, controlled trial is 480 subjects. The primary endpoints are Visual Analog Scale (VAS) pain score and the pain subsection of the Knee Injury and Osteoarthritis Outcomes (KOOS). The sample size calculations are based on improvements (from baseline to 1-year) in the visual analog scale (VAS) pain score and total KOOS. Total KOOS was used as a proxy and should ensure that the study is amply powered.

Assuming a decline of 1 point on average in pain in the Control arm (corticosteroids) and a decline on average of 2.5 points in a treatment arm (mesenchymal stem cells) and an estimated standard deviation on change of 3.5, the proposed sample sizes (n=121 subjects

per group or 484 total subjects) will provide 91% power to detect a difference on change of 1.5 points at the two-sided 5% significance level if the true difference between treatment groups is 1.5 points (two-sided two-sample equal variance t-test).

Assuming an increase of 10 points on average in total KOOS in the Control arm (corticosteroids) and an increase on average of 20 points in a treatment arm (mesenchymal stem cells) and an estimated standard deviation on change of 20, the proposed sample sizes (n=121 subjects per group or 484 total subjects) will provide 97% power to detect a difference on change of 10 points at the two-sided 5% significance level if the true difference between treatment groups is 10 points (two-sided two-sample equal variance t-test).

Each of the four participating sites will accrue 30 subjects to each of the 4 treatment groups. Cohort retention is expected to be 90% at 1-year.

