Sample Size	Total of 480 subjects. 120 subjects at each of the 4 institutions.
Statistical Analysis	The sample size calculations for the proposed intention-to treat, parallel-group, multicenter, randomized, controlled trial is based on improvements (from baseline to 1-year) in the visual analog scale (VAS) pain score and the knee injury and osteoarthritis outcome (KOOS) score. As the pain subsection of the KOOS is more sensitive and specific, using the full KOOS score as a proxy should provide ample power for the study.
Study Treatment	
Subjects will be divided among three parallel arms for ease of blinding.
 
Arm 1 includes randomization to bone marrow derived MSCs versus corticosteroid injection.
 
Arm 2 includes randomization to adipose derived MSCs versus corticosteroid injection.
 
Arm 3 includes randomization to umbilical cord tissue MSCs versus

	corticosteroid injection.
Study Evaluations	Follow-up exams will occur at intervals of 7 days, 1 month, 3 months, 6 months, and 9 months (telephone only), and 1 year. Subjects will undergo a pre-injection MRI and a follow-up MRI at 6 and 12 months. Total of 3 MRIs per subject. Subject will complete PROs at each time point.
Study Period	All randomized subjects will be followed in the study for approximately 1 year after treatment. If subjects continue to show improvement at the 1-year time frame, additional funding may be sought to provide ongoing treatment.

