### **6.2.2 Implementation of Randomization and Blinding**

Subjects randomized to Arm 1 or Arm 2 will undergo a procedure (bone marrow aspiration or liposuction) but will only receive one of the possible injections. For instance, subjects randomized to the control portion of Arm 1 will undergo a bone marrow aspiration but will receive a blinded corticosteroid injection. The bone marrow aspirate will still be processed and used to help quantify cell characteristics. Subjects randomized to Arm 3 will not undergo the procedures mentioned above. They will be blinded and receive either the stem cell injection or the corticosteroid injection.

Four hundred eighty subjects will be randomly assigned to treatment in this multicenter trial. Subjects at each clinical site will be randomized to ensure the trial is single-blind with a 1:1 allocation ratio across the four treatment groups.

One hundred twenty subjects will be randomized at each of 4 clinical sites. Arm 1: Forty subjects will be randomized with a 3:1 allocation ratio (bone marrow derived MSCs versus corticosteroid injection; 30:10). This same implementation plan will be used to randomize 40 subjects to Arm 2 (adipose derived MSCs versus corticosteroid injection) with a 3:1 allocation ratio and to randomize 40 subjects to Arm 3 (umbilical cord tissue MSCs versus corticosteroid injection) with a 3:1 allocation ratio.

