### **9.3 Efficacy Analyses**

The statistical analysis plan (SAP) has been developed and describes the subject populations to be included in the analyses, and procedures for accounting for missing, unused, and spurious data. This section is a summary of the planned statistical analyses of the primary and secondary endpoints.

The primary analysis of the data will be performed according to subjects' original treatment assignment (i.e., intention-to-treat analyses) regardless of their compliance to treatment and the inclusion of all data from all subjects randomized in the final analysis.

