#### **9.3.2 Primary and Secondary Efficacy Analyses**

Eight separate repeated-measures analysis will be performed on the eight efficacy variables described above. Each of the eight variables will be used as a dependent variable. The following model building method will be used for each analysis. Using Statistical Analysis System (SAS) MIXED Procedure (version 9.4; SAS Institute, Cary, NC), a linear mixed model will be fit on each efficacy variable. The model will include site, treatment arm, time on study (baseline and 1, 3, 6, 9

and 12 months on study), and treatment arm by time interaction as fixed effects. Subject ID will be the random effect. A compound-symmetric variance-covariance form in repeated measurements will be assumed and robust estimates of the standard errors of parameters will be used to perform statistical tests and construct 95% confidence intervals. The model-based means are unbiased with unbalanced and missing data, assuming missing data are non-informative. A P-value  $\leq 0.05$  will be considered statistically significant for all the terms in the mixed model. The statistical test for interaction between time on study and treatment will be the overall hypothesis test to determine whether efficacy variables in the four treatment arms changed significantly during 12 months of follow-up. If mean scores in the treatment arms are consistently different or similar over time (i.e., no statistical interaction) then the main effect test for treatment will be used as the primary hypothesis test to compare the treatment arms. The primary study results from this model will be the mean score and 95% confidence interval for each of the 4 treatment arms and the treatment mean differences and 95% confidence intervals.

Assuming a significant treatment effect on efficacy score change is identified (i.e., the interaction test is significant at  $P = 0.05$ ) then the six pairwise treatment comparisons on pain score change will be performed. A Bonferroni correction ( $p=0.05/6=0.0083$ ) for multiple comparisons will be applied. Specific statistical tests on efficacy score change will be done within the framework of the mixed effects linear model. All statistical tests will be 2-sided and adjusted for multiple comparisons. The same Bonferroni method will be used if the statistical interaction between treatment group and time on study is not significant but the main effect test for treatment is significant.

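### Section 9.2 gives power at two-sided 0.05 with 121 per group, but section 9.3.2 tests each pair at 0.0083 with 120 randomised: power for 1-year change is about 69–74% (VAS) and 84–89% (total KOOS), not 91% and 97%

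*Combined protocol and SAP*

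**What the plan says.** Section 9.2 bases the sample size on change from baseline to 1 year, compared between one cell arm and corticosteroid by a two-sided, equal-variance, two-sample t-test. For VAS it assumes mean declines of 2.5 and 1 points and a standard deviation of change of 3.5. It concludes that 121 per group (484 in total) "will provide 91% power to detect a difference on change of 1.5 points at the two-sided 5% significance level". For total KOOS, used as a proxy for the KOOS pain score, it assumes gains of 20 and 10 points and a standard deviation of 20, and states 97% power at the same level and sample size.

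The same section also says "Each of the four participating sites will accrue 30 subjects to each of the 4 treatment groups", which is 4 × 30 = 120 per group, and "Cohort retention is expected to be 90% at 1-year". The synopsis ("Total of 480 subjects. 120 subjects at each of the 4 institutions") and section 6.2.2 ("Four hundred eighty subjects will be randomly assigned to treatment in this multicenter trial") agree on 480.

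Section 9.3.2 starts with a treatment-by-time interaction test at 0.05. If that is significant, "then the six pairwise treatment comparisons on pain score change will be performed", each at 0.05/6 = 0.0083. It adds: "The same Bonferroni method will be used if the statistical interaction between treatment group and time on study is not significant" but the treatment main effect is. A pairwise claim therefore has to clear 0.0083 on either route.

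**The concern.** The power statement and the analysis describe different tests. Section 9.2 powers a single two-group comparison at 0.05; section 9.3.2 allows that comparison to count only at 0.0083. Section 9.2 also uses one more subject per group than the trial randomises, and makes no allowance for the loss it expects.

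Section 9.2 is the only place in the supplied text that gives power figures, and nothing there gives power at 0.0083. The synopsis sets out to identify a superior cell source and show its advantage over corticosteroid, which is a pairwise claim. A reader of a non-significant VAS comparison would judge it against a 9% chance of having missed the planning effect, when at the threshold actually used that chance is about three times as large.

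**Working it through.** **Inputs, all from sections 9.2 and 9.3.2.** VAS: difference Δ = 2.5 − 1 = 1.5, SD of change 3.5. Total KOOS: Δ = 20 − 10 = 10, SD 20. Per group: n = 121 (stated), 120 (randomised), 120 × 0.9 = 108 (retained). Two-sided α: 0.05 (section 9.2) and 0.05/6 = 0.0083 (section 9.3.2).

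**Formula.** Noncentrality δ = Δ / (SD × √(2/n)); df = 2n − 2; power = P(|T| > t(1 − α/2, df)), where T is noncentral t with parameter δ.

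**Reproducing the plan (n = 121, α = 0.05, critical value 1.970).**
- VAS: δ = 1.5 / (3.5 × √(2/121)) = 3.33; power 91.3%. Stated: 91%.
- Total KOOS: δ = 10 / (20 × √(2/121)) = 3.89; power 97.2%. Stated: 97%.

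So section 9.2 is correct on its own terms, and those terms contain no allowance for loss.

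**Changing to the planned conditions.** At α = 0.0083 the critical value rises to about 2.66.

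| n per group | α | VAS δ | VAS power | KOOS δ | Total KOOS power |
|---|---|---|---|---|---|
| 121 | 0.05 | 3.33 | 91.3% | 3.89 | 97.2% |
| 120 | 0.05 | 3.32 | 91.1% | 3.87 | 97.1% |
| 108 | 0.05 | 3.15 | 88.0% | 3.67 | 95.5% |
| 121 | 0.0083 | 3.33 | 74.9% | 3.89 | 88.9% |
| 120 | 0.0083 | 3.32 | 74.4% | 3.87 | 88.6% |
| 108 | 0.0083 | 3.15 | 68.6% | 3.67 | 84.3% |

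The threshold alone costs 91.3 − 74.9 = 16.4 points on VAS. Going from 121 to 120 costs a fraction of a point. The retention loss costs about 6 points at 0.0083 (74.4 − 68.6 = 5.8).

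**Partial data.** The mixed model keeps the earlier visits of subjects who drop out. The documents give neither a dropout pattern nor a within-subject correlation, so I assumed 2% lost before each of the five follow-up visits (10% in all), compound symmetry and correlation 0.2 to 0.7. Generalised least squares for month 12 minus baseline then gives an effective n of 111.6 to 112.8 per group. Power is 70.5–71.1% (VAS) and 85.7–86.2% (total KOOS), between the 108 and 120 rows.

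**Other contrasts.** Section 9.3.2 does not name month 12 for the pairwise tests. Suppose the 1.5-point VAS effect were constant from month 1 (an assumption).
- Mean of the five follow-up visits minus baseline: variance (3.5²/2) × (1 + 1/5) = 7.35, SD 2.71. By normal approximation, power at 0.0083 is 92.3% (n = 108) to 95.0% (n = 120).
- Treatment main effect with baseline kept as one of six time levels, as the model is written: effect 1.5 × 5/6 = 1.25, variance of a subject's mean σ²(1 + 5ρ)/6 with σ² = 3.5²/(2(1 − ρ)). With n = 120, power at 0.0083 runs from nearly 100% (ρ = 0.2) through 84% (ρ = 0.5) to 44% (ρ = 0.7).

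**The case against.** The strongest reply is that the pairs are only the second step. The plan's overall tests, the interaction or else the treatment main effect, are made at 0.05. A four-group F test on 1-year VAS change, a rough stand-in for that first step, has about 94% power at 120 per group and 91% at 108 if all three cell arms, or just one, beat corticosteroid by 1.5 points. If all three truly do, the chance that at least one clears 0.0083 is about 90%. This stands as a limit on scope: 69–74% is the power for one named pair, not for the overall test. It does not rescue the stated figures, because section 9.2 powers a two-group t-test and not an overall test. Requiring the F test first lowers pairwise power by less than 0.2 points in those two scenarios.

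It can also be said that the pairwise contrast need not be month 12. That is true, and under a visit-averaged contrast power could be higher or lower, as shown above. But section 9.2 chose 1-year change, so that is the like-for-like comparison.

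Intention-to-treat analysis is a further reply: section 9.3 calls for "the inclusion of all data from all subjects randomized in the final analysis". Including everyone randomised does not supply missing 1-year values, and with no loss at all VAS power is still only 74.4%.

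Finally, section 9.3 refers to a developed SAP, of which it is a summary. A power statement at 0.0083 in a separate document cannot be excluded, but section 9.2 would still disagree with 9.3.2 and with the 480 total.

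**Conclusion.** The concern holds. The 91% and 97% are correct arithmetic for a test the plan does not use for its pairwise claims. For a single cell-versus-corticosteroid comparison of 1-year change at 0.0083, power is 68.6–74.4% for VAS and 84.3–88.6% for total KOOS. The lower ends assume that only the 108 retained per group contribute; the upper ends assume that all 120 do. The Bonferroni threshold accounts for most of the drop, and 121 versus 120 is a minor inconsistency.

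The result rests on the protocol's own effects and standard deviations and on the 1-year contrast. The figures are per pair and per endpoint, so power to succeed on both co-primary endpoints would be lower than for VAS alone. No effect or standard deviation is given for the KOOS pain score, so power for that co-primary endpoint cannot be checked directly. This should be fixed, but it does not affect type I error control.

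**What to change.** In section 9.2:
- Replace 121/484 with 120/480.
- State power at two-sided 0.0083 as about 69–74% for VAS and 84–89% for total KOOS, with the retention assumption behind each end (108 or 120 per group contributing).
- Say that these are for one pairwise comparison of change from baseline to 1 year.

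This is a wording change. Enrolment, analysis and type I error control stay as they are, and the restatement itself calls for no extra subjects. The cost is a less favourable power statement, and whether that power is acceptable is for the sponsor to judge. For reference, keeping the stated power at 0.0083 would take 175 evaluable per group for 91% on VAS (175/0.9, or 195 randomised) and 166 for 97% on total KOOS (166/0.9, or 185 randomised).

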### **9.3 Efficacy Analyses**

The statistical analysis plan (SAP) has been developed and describes the subject populations to be included in the analyses, and procedures for accounting for missing, unused, and spurious data. This section is a summary of the planned statistical analyses of the primary and secondary endpoints.

The primary analysis of the data will be performed according to subjects' original treatment assignment (i.e., intention-to-treat analyses) regardless of their compliance to treatment and the inclusion of all data from all subjects randomized in the final analysis.

#### **9.3.1 Efficacy Variables**

##### **Primary efficacy variables:**

- Visual Analog Scale (VAS) pain score
- KOOS Pain Score

##### **Secondary efficacy variables:**

- Total KOOS Score
- KOOS Symptoms Score
- KOOS ADL Score
- KOOS Sports/Recreation Score
- KOOS Quality of Life (QoL) Score
- European Quality of life Score (EQ5D 3L) Index

#### **9.3.2 Primary and Secondary Efficacy Analyses**

Eight separate repeated-measures analysis will be performed on the eight efficacy variables described above. Each of the eight variables will be used as a dependent variable. The following model building method will be used for each analysis. Using Statistical Analysis System (SAS) MIXED Procedure (version 9.4; SAS Institute, Cary, NC), a linear mixed model will be fit on each efficacy variable. The model will include site, treatment arm, time on study (baseline and 1, 3, 6, 9

and 12 months on study), and treatment arm by time interaction as fixed effects. Subject ID will be the random effect. A compound-symmetric variance-covariance form in repeated measurements will be assumed and robust estimates of the standard errors of parameters will be used to perform statistical tests and construct 95% confidence intervals. The model-based means are unbiased with unbalanced and missing data, assuming missing data are non-informative. A P-value  $\leq 0.05$  will be considered statistically significant for all the terms in the mixed model. The statistical test for interaction between time on study and treatment will be the overall hypothesis test to determine whether efficacy variables in the four treatment arms changed significantly during 12 months of follow-up. If mean scores in the treatment arms are consistently different or similar over time (i.e., no statistical interaction) then the main effect test for treatment will be used as the primary hypothesis test to compare the treatment arms. The primary study results from this model will be the mean score and 95% confidence interval for each of the 4 treatment arms and the treatment mean differences and 95% confidence intervals.

Assuming a significant treatment effect on efficacy score change is identified (i.e., the interaction test is significant at  $P = 0.05$ ) then the six pairwise treatment comparisons on pain score change will be performed. A Bonferroni correction ( $p=0.05/6=0.0083$ ) for multiple comparisons will be applied. Specific statistical tests on efficacy score change will be done within the framework of the mixed effects linear model. All statistical tests will be 2-sided and adjusted for multiple comparisons. The same Bonferroni method will be used if the statistical interaction between treatment group and time on study is not significant but the main effect test for treatment is significant.

Missing values will be excluded from the repeated measures analyses. Unknown values for ethnicity and gender will be included as a separate unknown category in the models if they represent more than 5% of the subjects.

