### **9.3.3 Efficacy Analyses across Subgroups**

The heterogeneity of treatment effects across age, sex, and ethnicity will be evaluated using a statistical test for interaction terms. Specifically, effects of treatment in subgroups will be determined by including the additional interaction terms between treatment and the three subgroups (age, sex, and ethnicity) in the repeated measures model described above for the eight efficacy variables.

The following variables will be treated as categorical variables in all of the linear mixed models.

- Treatment arms: CSI (reference), BMAC, ADP, UCT
- Age:  $\leq 65$  (reference) vs.  $>65$
- Sex: female vs male (reference)

- Ethnicity: Hispanic vs non-Hispanic
- Time: 0, 1, 2, 3, 4, 5 representing baseline and 1, 3, 6, 9 and 12 months follow-up visits

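### The efficacy model compares change from baseline without adjusting for the baseline score, which is valid but generally less precise than adjustment

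*Combined protocol and SAP*

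**What the plan says.** Section 9.3.2 fits a linear mixed model to each of eight efficacy variables. "The model will include site, treatment arm, time on study (baseline and 1, 3, 6, 9" and 12 months), "and treatment arm by time interaction as fixed effects". Subject is a random effect. The covariance is restricted: "A compound-symmetric variance-covariance form in repeated measurements will be assumed", with robust standard errors.

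Section 9.3.3 makes time categorical, with baseline as level 0: "Time: 0, 1, 2, 3, 4, 5 representing baseline and 1, 3, 6, 9 and 12 months follow-up visits". CSI is the reference arm.

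The arm-by-time interaction is the overall test. If it is significant, "the six pairwise treatment comparisons on pain score change will be performed", at 0.05/6 = 0.0083. If it is not, "then the main effect test for treatment will be used as the primary hypothesis test to compare the treatment arms".

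Section 9.2 sizes the trial on change from baseline to 1 year. For VAS it takes a 1.5-point difference and "an estimated standard deviation on change of 3.5"; for total KOOS, a 10-point difference and an SD of 20.

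Nowhere in the supplied text are the arm means set equal at baseline or the baseline score entered as a covariate. Site is the only adjustment. Section 9.3 calls itself a summary of a SAP, but the supplied text contains no fuller account.

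**The concern.** The schedule of activities and Section 8.1.1 place the patient-reported outcomes at screening, before randomisation. The four arms therefore have equal expected baseline means. A model with a free baseline mean in each arm does not use that fact. It subtracts baseline with a coefficient fixed at 1, whatever the data say about how strongly baseline predicts month 12.

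At stake are the width of the intervals and the power of all six pairwise comparisons on the eight variables, and protection against chance baseline imbalance. When the true regression slope is below 1, a change score over-corrects such an imbalance; when it is above 1, it under-corrects.

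The fallback test raises a related matter. It averages the arm difference over all six modelled visits, including one at which no treatment has been given.

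**Working it through.** **Reproducing the plan's power.** Inputs are from Section 9.2: 121 per group, two-sided 5%, two-sample t-test on change.
- VAS, difference 1.5, SD 3.5: 91.3% (stated 91%).
- Total KOOS, difference 10, SD 20: 97.2% (stated 97%).

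Both reproduce. At the planned 120 per group, VAS power is 91.1%.

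**What the planned model estimates.** With complete data and equal numbers of each arm at each site, the arm-by-month-12 term is the difference between arms in raw mean change. Fitting the model to simulated complete data confirmed this to five decimals (0.06953 both ways at r = 0.5). With about 10% dropout the two differ slightly (0.244 against 0.256).

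**Variance comparison.** Let s0 and s1 be the SDs at baseline and month 12, r their correlation, and n the number per group.
- Change score: (2/n)(s0² + s1² − 2·r·s0·s1)
- Baseline-adjusted, slope estimated freely: (2/n)·s1²(1 − r²)
- Difference: (2/n)(s0 − r·s1)², which is never negative and is zero when s0 = r·s1.

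**Case A: equal variances** (implied by the plan's compound symmetry). The ratio is (1 − r²)/[2(1 − r)] = (1+r)/2. The documents do not give r, so 0.3 to 0.7 is assumed. Change SDs are held at 3.5 and 20, with n = 121.

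| r | Variance ratio | SE reduction | VAS power, 5% | KOOS power, 5% | VAS power, 0.0083 |
|---|---|---|---|---|---|
| unadjusted | 1 | – | 91% | 97% | 75% |
| 0.3 | 0.65 | 19% | 98% | 99.8% | 93% |
| 0.5 | 0.75 | 13% | 97% | 99.4% | 88% |
| 0.7 | 0.85 | 8% | 95% | 98.8% | 83% |

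With about 10% dropout the simulated ratios are 0.67, 0.77 and 0.86.

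**Case B: VAS with a restricted baseline.** Equal variances and a change SD of 3.5 imply s0 = 3.5/√[2(1 − r)] = 2.96, 3.50 or 4.52. Inclusion criterion 6 requires an average daily VAS of at least 3. Assume a 0–10 scale (the range is not stated) and baseline scores that respect the floor. The largest possible SD is then 3.5, with half at 3 and half at 10; a uniform spread gives 7/√12 = 2.02. Taking s0 = 2.02 and solving s0² + s1² − 2·r·s0·s1 = 3.5² = 12.25 for s1:

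| r | s1 | s1²(1 − r²) | Variance ratio | SE reduction | VAS power, 5% | VAS power, 0.0083 |
|---|---|---|---|---|---|---|
| 0.3 | 3.53 | 11.33 | 0.92 | 4% | 93% | 79% |
| 0.5 | 4.04 | 12.25 | 1.00 | 0% | 91% | 75% |
| 0.7 | 4.60 | 10.81 | 0.88 | 6% | 94% | 81% |

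**Constraining baseline under compound symmetry.** Suppose baseline stays a response with a common mean and compound symmetry is kept. The baseline slope is then forced to the pooled correlation, b = (average covariance)/(average variance). Using Case B's SDs, with every pair of visits correlated r and s1 at all follow-ups, b = 0.29, 0.48 and 0.66. The variance s1² + b²s0² − 2·b·r·s0·s1, divided by 12.25, is 0.94, 1.09 and 1.17. Precision is worse than the plan's in two of the three cases.

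**Fallback main effect.** A constant post-baseline effect d averages to (0 + 5d)/6 = (5/6)d over the six visits. Under compound symmetry with equal variances and unit SD, its standardised size is (5/6)/√[(1+5r)/6]. For baseline-adjusted follow-up visits it is 1/√[(1+4r)/5 − r²]. The quotient is 0.76, 0.65 and 0.50 at r = 0.3, 0.5 and 0.7.

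**The case against.** The strongest reply is that nothing here is wrong. A repeated-measures model with free baseline means is valid. The sample size uses the SD of change, so design and analysis agree, and the stated powers reproduce. That stands: this is a point about efficiency, not bias.

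Three stronger readings are tempting and should be resisted.

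- A reader might infer that baseline buys no precision at all. It does buy some. Under equal variances, a month-12-only comparison has variance 1/[2(1 − r)] times that of the change score: 0.71, 1.00 and 1.67 at r = 0.3, 0.5 and 0.7. Subtracting baseline helps above r = 0.5 and hurts below it.
- A reader might apply (1+r)/2 to VAS and read it as a gain worth 18% to 54% more subjects (1/0.85 and 1/0.65). Those figures need equal variances, which the entry floor makes doubtful. Under the scale and floor assumptions above, equal variances at r = 0.7 would need an impossible baseline SD, and r = 0.5 sits at the extreme bound. The floor concerns VAS only; there is no such criterion for the KOOS scores or EQ5D.
- A reader might carry (1+r)/2 over to whichever test is used. The fallback main effect is not a change score, so that ratio does not describe it; its problem is the 5/6 dilution.

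The drop in VAS power from 91% to 75% at the 0.0083 level is a separate multiplicity matter and is not caused by the handling of baseline. At 5% the Case A gain for VAS is from 91% to between 95% and 98%. A fuller SAP, if it exists, might also already adjust for baseline.

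**Conclusion.** The point holds as one of efficiency. As written, the pairwise tests on change are essentially unadjusted change-score contrasts. Baseline adjustment with a freely estimated slope is, in large samples, never less precise and usually more so.

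The size rests on quantities that the documents do not give. With equal variances and r from 0.3 to 0.7, adjustment cuts the variance by 15% to 35%. For VAS, with an assumed baseline SD of 2.02 and the plan's change SD, the cut is 0% to 12%. The KOOS pain score, the other primary variable, has no SD in the plan; the KOOS figures above are for the total score.

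The 5/6 dilution of a sustained effect in the fallback test does not depend on r. The documents do not support a claim that the stated power is wrong or that the planned estimates are biased. The change is worth making because the data are already collected.

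**What to change.** In Section 9.3.2, for all eight variables, take baseline out of the response. Model months 1, 3, 6, 9 and 12 with the baseline score, baseline-by-visit, site, arm, visit and arm-by-visit. Base the overall test, the fallback main effect, the pairwise tests and the subgroup terms of Section 9.3.3 on the post-baseline arm effects.

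The overall test must be restated. Once baseline is no longer a time level, arm-by-visit asks only whether the effect varies over follow-up, so a constant benefit would not show in it. A joint test of all post-baseline arm effects has 3 × 5 = 15 degrees of freedom, the same as the planned interaction, (4 − 1) × (6 − 1) = 15.

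Alternatively, keep baseline as a response with a mean common to the four arms, but replace compound symmetry with an unstructured covariance (6 × 7/2 = 21 parameters, from 480 subjects). The two options are not interchangeable if compound symmetry is kept, as the working shows.

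Cost: no new data and no extra subjects, but more than one sentence, because the interaction, main-effect and subgroup tests all need rewording. The covariate version leaves out subjects with no post-baseline score, which sits awkwardly with Section 9.3's commitment to include everyone randomised. The common-mean version keeps them. The choice should be fixed before unblinded data are seen.
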